Cystic fibrosis Transmembrane (CFTR) modulators are a relatively new development in management of people with cystic fibrosis (pwCF) and represent a paradigm shift; this therapy directly affects the malfunctioning protein responsible for CF as opposed to conventional management options which seek to treat the consequences of the condition. This in combination with the current model of CF care is resulting in improved life expectancy and quality of life for many pwCF.

An important part of preserving pwCF's health is a once yearly review process called annual review; this a nationally recognised process although there may be some regional variation in practice. Annual review is a detailed assessment of every aspect of the patient's condition including a face-to-face review. At Liverpool Heart and Chest Hospital (LHCH) routine clinical care currently includes a dynamic chest x-ray and spirometry as part of this process

Previous Work with DCR in relation to pulmonary Function

Prior work has established that some DCR metrics correlate with some measures of lung function. For example, projected lung area has been demonstrated to correlate with total lung capacity. Furthermore, diaphragm motion has been shown to correlate with vital capacity and FEV1 in non – CF healthy volunteers.

Further work conducted in our large adult CF centre at LHCH has demonstrated significant improvement in changes in diaphragm movement and change in projected lung area in those treated for exacerbations of cystic fibrosis. In a smaller study here at LHCH in a CF cohort DCR metrics have also been shown to correlate with measures of lung volume. This work also demonstrated that the DCR procedure was well tolerated by the CF population and the procedure acquisition time proportional to a standard posteroanterior (PA) x-ray.

DCR as an assessment of pulmonary function

DCR provides an assessment of structures involved in respiration over time period and therefore could provide us with alternative insights into respiratory function. It may be possible that relating DCR to conventional lung function testing allows it to be used as a surrogate tool to measure some of these parameters used to assessment pulmonary function. Alternatively, it may provide different parameters of lung function which don't directly correlate with conventional testing, but in of themselves are clinically relevant.

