Null hypothesis: there is no relationship between variables recorded by dynamic chest x-ray and that calculated by spirometry in people with CF.

Alternative hypothesis: We can correlate the findings on DCR with that of recorded spirometry findings.

Alternative hypothesis: there is a correlation between dynamic chest x-ray and that calculated by Spirometry in people with CF

Funding

This Study has received no specific resources from any funding agency either public or commercial.

Konica Minolta have provided a grant in kind with the dynamic x-ray machine, workstation and imaging software and technical support. Konica Minolta does not have any input in the clinical acquisition of data from relevant patient group.

Method and analysis

Study Setting

Single centre study based at Liverpool Heart and Chest Hospital. From a practical perspective the best place for the study given:

1. Dynamic x-ray machine is novel and located on site here
2. Tertiary centre for adult cystic fibrosis.

Part A : Real-time paired DCR and Spirometry in Healthy control Group

Aim: Explore relationship between the Dynamic CXR imaging and simultaneous spirometry in a healthy population with no known underlying lung condition.

Study design: The study involves the recruitment of healthy volunteers from general population. We would aim to recruit n=100 participants. The key investigations are Dynamic chest x-ray and paired spirometry as outlined below. Individuals will be recruited through a poster campaign successful in previous studies

Part B: Real-time paired DCR and spirometry in a CF subgroup.

Aim: Explore relationship between the Dynamic CXR imaging and simultaneous spirometry in a CF population

Study Design: This aspect of the study involves recruitment pwCF to perform DCR with paired spirometry, aiming to recruit n= 100 people. The above format would be repeated with paired spirometry and DCR in CF subgroup of LHCH patients. CF patients at LHCH attend a once yearly review process called annual review. The current format already includes a dynamic chest x-ray and spirometry as part of this Process (although not simultaneous). Through CF data base co-ordinator, a letter will be provided to all pwCF if interested.

This would allow for a Direct comparison of spirometry with DCR data. Furthermore, it therefore also allows for a comparison of Comparison with the control group. The structure of how these investigations are performed is outlined below.

Part C:

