Subjects will perform spirometry in upright seated position which chest resting forward on the flat panel of the chest x-ray machine. The Spirometry instructions are given by a pulmonary physiologist who call out instructions. Spirometry requires a a deep inspiration followed by a maximal expiration into a hand held tube device. All pulmonary physiologists conducting the research at LHCH are accredited with the association for respiratory technology and physiology practioners(ARTP) and with the registration council for clinical physiologists (RCCP). The first 2 attempts will be spirometry only (as opposed to DCR). This is inline American Thoracic Society/European Respiratory Society repeatability and acceptability criteria (see below) and will allow a comparison with third spirometry attempt. The two non-DCR manoeuvres will facilitate volunteer comfort with the technique and allow for further coaching if required before the DCR image is captured. The third 'live' attempt will be recorded in conjunction with a DCR. The investigator tells the radiographer when to start recording the x-ray and breathing instructions are called out as per conventional Spirometry instructions.

All Spirometry will be reviewed by LHCH pulmonary physiologists and be entered on a clinical master datasheet. The following are the key Data points which will be recorded for the spirometry attempt with DCR (absolute and percentage predicted values):

- FEV1
- FVC
- FEV-1/FVC ratio

Table 3: ATS/ERS Repeatability and Acceptability Criteria

Spirometry	
Spirometry Within-Manoeuvre Criteria	Spirometry Between-Manoeuvre Criteria

*3x Acceptable flow volume loops performed free from significant artefact including;
Cough during first second of exhalation, Glottis closure that influences the measurement
Early termination or cut-off, Not maximal effort, Leak, Obstructed mouthpiece
Duration ≥ 6s or until a plateau in the volume-time curve or if the subject cannot or should not continue to exhale*

*The two largest values of FEV1 must be within 0.150L of each other
The two largest values of FVC must be within 0.150L of each other*

Dynamic Chest X-ray

Dynamic chest x-rays are performed in the x-ray room in Liverpool heart and chest Hospital. This is simultaneous with spirometry so will occur in the same place.

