- Current exacerbation

Spirometry exclusion criteria (same as for Group A, see above)

Statistical analysis

Statistical analysis will be carried using the R software package, produced and supported by the R Foundation for Statistical Computing, under the GNU GPL v2 public license.

All data will be collated electronically and stored on a secure server in line with data protection.

Two-sided P-values of <0.05 will be considered as statistically significant. Confidence intervals will be presented where appropriate and feasible.

Comparison of the data will be primarily between dynamic chest x-ray results and spirometry data. Depending on the distribution of the dataset, paired t-tests or the relevant non-parametric equivalent will be used to analyse within groups. Categorical data will be presented as frequency and percentage. Continuous data will be presented as number of observations, mean, standard deviation, median and interquartile range as appropriate.

Proposed timetable of events

- **December 2022** – Start of Protocol write up.
- **January 2023** – research proposal submission to local research committee
- **March 2023**- Sure group review and revisions to protocol and study literature
- **July 2023** -Iras application
- **September 2023 to September 2024** - Data collection is projected to take around 365 days, aiming for completion end of July 2023. This allows for the recruitment of 2 ‘healthy volunteers’ and 2 people with CF a week.
- **September to October 2024**- Data analysis
- **October/November/December 2024**- write up of research results +/- publication

Figure 3 – Gantt Chart of Projected Timetable December 2022 – December 2024

Task	D	J	F	M	A	M	J	J	A	S	O	N	D	J	F	M	A	M	J	J	A	S	O	N	D
Protocol Write up	█	█	█	█	█	█	█																		
R&I committee meeting LHCH		█																							
Sure Group review				█	█	█	█																		
Iras Application							█	█	█																
Study period										█	█	█	█	█	█	█	█	█	█	█	█	█	█	█	
Data analysis																						█	█		
Results write up																							█	█	█

Safety

Ionising Radiation

This study requires exposure to ionising radiation.

We are exposed to radiation in our daily lives and our annual average radiation exposure in the UK is 2.7mSv

An example of typical radiation doses from clinical investigations are included below.

Table 4 - Effective Doses for Common Radiological Examinations

Projection	Estimated effective dose (mSv)
Chest PA	0.014
Chest lateral	0.038

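### The hypotheses and the p<0.05 threshold set no minimum strength of relationship, so a significant correlation alone could not show how DCR compares with spirometry or support surrogate use

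*Combined protocol and SAP*

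**What the plan says.** The hypotheses that close the Aims section set a null of no relationship against an alternative of some relationship. For CF the null is that "there is no relationship between variables recorded by dynamic chest x-ray and that calculated by spirometry in people with CF" and the alternative is that "there is a correlation between dynamic chest x-ray and that calculated by Spirometry in people with CF". The more general alternative reads "We can correlate the findings on DCR with that of recorded spirometry findings". None gives a size.

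The Statistical analysis section supplies the one threshold: "Two-sided P-values of <0.05 will be considered as statistically significant". It promises confidence intervals only where suitable and practicable. It names paired t-tests or a non-parametric counterpart for within-group work. It names no correlation coefficient, regression model, agreement limit or prediction error.

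Each cohort has a target of 100: "We would aim to recruit n=100 participants" for Part A and "aiming to recruit n= 100 people" for Part B. Sample and Recruitment describes the work as exploratory, with no power calculation.

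On purpose, the Overview says that one key aim is to establish how DCR compares with spirometry. The section on DCR as an assessment of pulmonary function suggests that relating DCR to conventional testing possibly "allows it to be used as a surrogate tool to measure some of these parameters". It also offers an alternative: that DCR may supply different, clinically relevant information.

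**The concern.** Whether a correlation differs from zero is one question. How closely DCR tracks spirometry, or how well it estimates a person's FEV1, is another. The hypotheses and threshold address only the first, while the background motivates the study partly by the second. With no minimum strength and no planned measure of error, a result could be reported as a significant relationship in both cohorts and leave a reader unable to tell whether DCR carries much or almost no information about lung function. The data to answer that will have been collected. Only the analysis wording is missing.

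**Working it through.** The plan gives no power, target correlation or prediction error, so there is no figure of its own to reproduce. The check asks what the stated threshold implies.

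**Inputs from the plan:** n = 100 per cohort (Parts A and B); alpha = 0.05, two-sided (Statistical analysis).

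**Assumptions:**
- The hypotheses are tested with a Pearson correlation on one DCR–spirometry pair. The plan does not name this test.
- Evaluable pairs may fall to 70. The DCR procedure section says a suboptimal manoeuvre cannot be repeated, but gives no loss rate.
- The between-person SD of FEV1 is 0.8 L, range 0.6 to 1.0 L. The plan gives none.

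**Step 1. Smallest significant correlation.** r = t / √(n − 2 + t²), with t the 0.975 quantile on n − 2 degrees of freedom. For n = 100, t = 1.984, so r = 1.984 / √(98 + 3.94) = 0.197. A large-sample Spearman calculation, 1.96/√99, also gives 0.197.

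**Step 2. What that correlation conveys.** R² = 0.197² = 3.9%. Residual SD as a fraction of raw SD = √(1 − 0.039) = 0.980. Knowing the DCR value reduces the error by 2%. The Fisher 95% CI for r is about 0.00 to 0.38.

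**Step 3. Sensitivity to lost pairs.**

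| Evaluable pairs | Critical r | R² | Residual SD / raw SD |
|---|---|---|---|
| 100 | 0.197 | 3.9% | 98.0% |
| 90 | 0.207 | 4.3% | 97.8% |
| 80 | 0.220 | 4.8% | 97.6% |
| 70 | 0.235 | 5.5% | 97.2% |

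**Step 4. Weak true correlations are likely to be declared significant.** At n = 100, the true correlation detected with given power is tanh[(1.96 + z) / √97]. This is 0.28 for 80% power and 0.32 for 90%. They correspond to about 8% and 10% of variance.

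**Step 5. Illustration in litres.** Approximate 95% prediction half-width = 1.96 × SD × √(1 − r²), ignoring uncertainty in the fitted line. With SD = 0.8 L:
- no DCR information: 1.96 × 0.8 = ±1.57 L;
- r = 0.197: ±1.54 L;
- r = 0.5: ±1.36 L;
- r = 0.8: ±0.94 L.

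For SD from 0.6 to 1.0 L, the just-significant case runs from ±1.15 to ±1.92 L. The 98% ratio in Step 2 does not depend on the assumed SD.

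**The case against.** The strongest reply is that the plan does not claim what it would need to claim for this to be an error. The study is declared hypothesis-generating. The aims are to explore and investigate relationships, and surrogacy is one hedged possibility beside another. The X-ray machine Safety section says the images will not alter patient management. Confidence intervals are foreseen, and one running from about 0.00 to 0.38 would look weak to any reader. All of this stands, and it limits the point to an improvement in analysis and reporting.

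Four stronger readings are tempting, and the documents do not support them:

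- **That success is defined as p<0.05 on a correlation.** No section defines success or a rule for accepting the alternative. That reading comes from joining the Aims to the Statistical analysis section.
- **That the plan specifies a correlation test.** It names paired t-tests, which compare means and cannot address a correlation between measures in mm or area and measures in litres. That is a separate defect. Correcting the test alone would still leave no measure of strength or error.
- **That rejecting zero correlation adds nothing to prior work.** The FEV1 and vital capacity correlations cited are in healthy volunteers without CF, and the smaller CF study concerned lung volume. The plan also says that simultaneous measurement has not been done before.
- **That prediction error should meet the Table 3 limit.** The rule "The two largest values of FEV1 must be within 0.150L of each other" checks repeatability between one person's manoeuvres. It is not an accuracy limit for a different measurement.

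What the reply does not answer is that no conclusion is tied to the confidence intervals, their reporting is optional, and no quantity in litres is planned.

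**Conclusion.** The point holds as a gap in the analysis plan. The only hypotheses and the only threshold can be met by |r| of about 0.20 with 100 people, or about 0.235 with 70. That is 4% to 5.5% of variance, with residual SD 97% to 98% of raw. A significant result alone therefore cannot show how DCR compares with spirometry or support surrogate use. This rests on the hypotheses being tested by correlation, which the plan implies but does not specify, and on an assumed lower bound for evaluable pairs. The litre figures also need an assumed SD and are illustrative only. No data are invalidated and no stated decision rule is wrong. The change is worth making because it is cheap and limits what can be concluded from a significant p-value.

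**What to change.** In the Statistical analysis section, for each cohort:

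1. Regress absolute FEV1 and FVC, already recorded for the manoeuvre performed with DCR, on the named DCR measure(s).
2. Always report r with its 95% CI, removing the optional wording for this estimate.
3. Report the residual SD and 95% prediction interval in litres, cross-validated if several DCR measures are combined in one model.
4. State that any conclusion about surrogate use will rest on the prediction error and not on p<0.05.

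Do not adopt the 0.150 L repeatability criterion as an accuracy benchmark. Making cross-validated error the headline result is a matter of preference and is not required.

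The cost is a paragraph of text and a little more analysis in R, with no new data or visits. The downside is a possibly less favourable headline than a significant correlation.

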Retrospective Review of longitudinal DCR data with regards to clinical markers of CF status

Aim: To see how changes in key quantitative markers from DCR imaging relate to key CF clinical parameters

Study design: pwCF consenting for part B of the study will also be consented for using their current imaging as part of a longitudinal review of DCR imaging. Analyses will include an evaluation of the relationship between baseline DCR quantitative measurements and key clinical CF parameters that are recorded as part of their ongoing monitoring and care.

Schedule of Events

Below is highlighted a timetable for the schedule of events.

Table 1 – Schedule of Events for Healthy Volunteers

Contact	Purpose	Event	Duration
1	Indirect Contact	Individual contacts study team following poster campaign	N/A
1	Initial Direct contact	Provided with patient information sheet and consent information	20 minutes
2	Consent	Informed Consent taken	20 minutes
3	Attendance for imaging	Dynamic chest radiograph acquired with spirometry Completion of questionnaire	30 minutes

Table 2 – Schedule of Events for people with CF

Contact	Purpose	Event	Duration
1	Indirect Contact	Contacted via letter, patient information sheet enclosed	N/A
1	Initial Direct contact	Ensure provided with patient information sheet and consent information	20 minutes
2	Consent	Informed Consent taken	20 minutes
3	Attendance for imaging	Dynamic chest radiograph acquired with spirometry Completion of questionnaire	30 minutes

Once recruited the individual will attend for radiology department for the acquisition of the imaging and spirometry.

Dynamic chest X-ray procedure with paired spirometry

This study involves performing 2 simultaneous investigations – Dynamic x-ray and Spirometry, outlined below. For both parts of the Study A and B the process will be the same.

Spirometry:

Spirometry will be performed using validated and accredited spirometers that are used in clinical practice. The Study would utilise Geratherm® Spirostik™ spirometers (which can be Bluetooth or not) and documented using Geratherm® Blue Cherry™ software.

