The Figure below demonstrates the room set up. The study volunteer attends room 2 where our DCR machine in LHCH is placed. The individual sits on a stool facing the FPD. The Radiographer, researcher and any pulmonary physiologist are by the control station. The volunteer holds the spirometer to their mouth. When instructions for Spirometry are given the Radiographer presses the button to record the DCR. The complete spirometry attempt is completed, and the x-ray ceased when the full motion completed. The DCR machine will stop after 220 frames the exposure will not continue if the full spirometry is not completed.

Sample and Recruitment

This study is exploratory work and is ultimately hypothesis generating and as such no formal statistical power calculation has been carried out. Target recruitment numbers are therefore based on pragmatic assessment of the ability to recruit and measure successfully.

Recruitment Part A: The study involves the recruitment of healthy volunteers from general population. We would aim to recruit n=100 participants. Recruitment will be made through internal advertisement at LHCH hospital trust, University of Liverpool and Liverpool John Moore University

Recruitment Part B: People for part B of the study will be recruited through annual review process at CF clinic. As part of this process all people will undergo DCR and spirometry. They will be exposed to no further radiation, but it will mean that they have to perform an extra spirometry procedures. Individuals participating in part B will consent to using their investigation in part of the longitudinal review.

The Liverpool Heart and chest hospital has approximately 350 people with CF, however only 302 are present in the area (as opposed to being based in other areas which means they don't come to clinic). Transplanted individuals will be excluded (totalling 7) as well as pregnant individuals (currently 15). There is approximately 20% exacerbation rate and approximately 30% do not attend any given appointment. This would give us a projected population of just over 150 individuals to recruit from (please see Figure 2 below).

It is important to note that this is a conservative estimate pwCF who have a current exacerbation or who DNA appointment may return for their annual review study at a later date (however this may not be within the study recruitment period)

[figure not shown]
Consent

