Informed consent will be obtained prior to the participant undergoing enrolment in the study. A patient information sheet will be provided prior to taking informed consent.

The opportunity to ask questions will be given. Capacity will be assessed in order to determine that informed consent can be given.

Participation will be voluntary, and consent can be withdrawn at any time.

Figure 2 - CF cohort selection flow chart

Participation enrolment criteria:**Part A: Real-time paired DCR and Spirometry in Healthy control Group****Inclusion criteria:**

- Age: ≥ 17 years old and ≤ 50 years old
- and
- No underlying respiratory illness (chronic or acute)
- and
- Able to provide informed consent

Exclusion criteria**General exclusion criteria:**

Any of:

- Potentially pregnant or lactating
- Inability to provide informed consent
- Unable or unwilling to sit to perform DCR/Spirometry in the radiology department
- Unable or unwilling to follow Spirometry breathing instructions (e.g., holding breath or taking a deep breath)
- Unable to perform reproducible spirometry and/or full pulmonary function studies within ATS-ERS criteria
- Significant radiation exposure within the last year (for example, numerous CT scans of chest)
- Involved, either currently or recently, in other studies involved non-routine exposure to sources of ionising radiation
- Any serious or active medical or psychiatric illness, which in the opinion of the investigators, would interfere with subject treatment, assessment, or compliance with the protocol
- Inability to complete spirometry performance in 20 seconds.
- Current Chest infection

Spirometry exclusion criteria

Any of:

- Unstable cardiovascular status, recent MI or PE (within 6 weeks)
- Haemoptysis of unknown aetiology (within 6 weeks)
- Pneumothorax (present, or occurring within 6 weeks)
- Within 24 hours of bronchoscopy
- Thoracic, abdominal or cerebral aneurysm
- Recent eye surgery or increased intraocular pressure
- Recent thoracic or abdominal surgery
- Acute nausea, vomiting or diarrhoea
- Pregnancy
- Undergoing treatment for TB

- **Part B: Real-time paired DCR and spirometry in a CF subgroup**

Inclusion criteria:

- Age: ≥ 17 years old ≤ 50
and
- Attending the adult CF Unit at LHCH
and
- Confirmed CF diagnosis (positive sweat test in childhood and by genotyping)
and
- Able to provide informed consent

Exclusion criteria**General exclusion criteria, same as Group A (see above) plus:**

- Recipient of Lung transplant

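### Part C can mix exacerbation and stable films: only the Part B film must be exacerbation-free, so DCR changes can be shifted and DCR–FEV1 correlations inflated by acute illness

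*Combined protocol and SAP*

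**What the plan says.** The Part C aim is "To see how changes in key quantitative markers from DCR imaging relate to key CF clinical parameters". Its study design paragraph says that people consenting to Part B "will also be consented for using their current imaging as part of a longitudinal review of DCR imaging", and it names one analysis, of the "relationship between baseline DCR quantitative measurements and key clinical CF parameters". Sample and Recruitment adds, for Part B: "Individuals participating in part B will consent to using their investigation in part of the longitudinal review". The study film is therefore one point in the longitudinal series. The earlier points are existing films; the section on DCR as an assessment of pulmonary function says that DCR has been part of annual review at the centre since 2019. The same section gives the purpose as understanding lung health over time and asks whether DCR features predict future outcomes.

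The Part B exclusions include "Current exacerbation" and, carried over from Part A, "Current Chest infection". Part C has no eligibility criteria or film-selection rule of its own. The Statistical analysis section does not mention exacerbation status or treatment.

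Two other statements bear on this. The section on previous work reports "significant improvement in changes in diaphragm movement and change in projected lung area in those treated for exacerbations of cystic fibrosis". Sample and Recruitment says "There is approximately 20% exacerbation rate", and that people in exacerbation may come back later for the study.

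**The concern.** The protocol treats exacerbation as important enough to keep out of the Part B film, and its own earlier work indicates that DCR measures move with exacerbation treatment. Part C nevertheless accepts earlier films without asking what state the person was in. Two different things can go wrong.

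1. **Shift in the mean change.** If some earlier films were taken in exacerbation and the last one cannot be, the average change into the last film is pushed upwards. The Cystic Fibrosis section describes progressive decline in lung function, so the result could equally be a decline that is hidden.
2. **Induced or inflated correlation.** If exacerbation lowers both DCR measures and FEV1, people whose status differs between two films will show the two measures moving together, even when their stable-state changes are unrelated. This comes from status varying between films and does not need the last film to be restricted.

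At stake is the interpretation of Part C. A short-term illness effect could be reported as evidence that DCR tracks long-term lung health or predicts outcome.

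**Working it through.** **The plan's own figure.** Part C has no sample size or effect size to reproduce. The 20% is used once, in the projected recruitment pool: (302 − 7 − 15) × (1 − 0.20) × (1 − 0.30) = 156.8, which agrees with the stated figure of just over 150. In the protocol, then, 20% is a recruitment loss. Applying it to earlier films is an assumption.

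**Model.** Each earlier film falls in an exacerbation with probability p, independently between films; the Part B film never does. An exacerbation lowers both the DCR measure and FEV1 by d, in SDs of the stable between-film change. Stable changes have mean zero and are uncorrelated. Assumed inputs: p = 0.20 or 0.05, d = 0.5 to 1.5. The documents give no d, and no FEV1 response to exacerbation.

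**Formulas.**
- Mean shift into the Part B film: p × d. Between two earlier films: 0.
- Correlation into the Part B film: v/(1 + v), with v = p(1 − p)d². At p = 0.20, p(1 − p) = 0.16.
- Correlation between two earlier films: v/(1 + v), with v = 2p(1 − p)d². At p = 0.20, 2p(1 − p) = 0.32.

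**Results at p = 0.20.**

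| d | Mean shift into Part B film (SD) | r into Part B film | r between two earlier films |
|---|---|---|---|
| 0.5 | 0.10 | 0.04/1.04 = 0.04 | 0.08/1.08 = 0.07 |
| 1.0 | 0.20 | 0.16/1.16 = 0.14 | 0.32/1.32 = 0.24 |
| 1.5 | 0.30 | 0.36/1.36 = 0.26 | 0.72/1.72 = 0.42 |

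**Results at p = 0.05.** Here p(1 − p) = 0.0475. Into the Part B film, r = 0.0475/1.0475 = 0.05 at d = 1 and 0.107/1.107 = 0.10 at d = 1.5, with mean shifts of 0.05 and 0.075 SD. Between two earlier films, r is about 0.09 and 0.18.

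**What this does to a test at two-sided 0.05.** With n = 100 (the Part B target, so the most Part C can have) and 4,000 simulations, changes into the Part B film at p = 0.20 gave these rejection rates:
- d = 0.5: 17% for a paired t-test of change, 7% for the correlation.
- d = 1.0: 44% and 28%.
- d = 1.5: 74% and 77%.

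With both films at 20%, the t-test stayed at about 5%, while the correlation was declared significant in 11%, 68% and 99% of runs at d = 0.5, 1.0 and 1.5. With exacerbation films removed throughout, the rates were 5.2% and 5.4%.

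The two mechanisms are thus distinct: the restriction on the last film produces the mean shift but makes the induced correlation smaller.

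**The case against.** The strongest reply has five parts.

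- **The mean shift is not a stated target.** Part C asks how DCR changes relate to clinical parameters and specifies no test of mean improvement; the paired tests in the Statistical analysis section are generic. This stands, and it makes the correlation the more important effect. The shift matters only if average change into the Part B film is reported.
- **The co-movement is real.** If DCR and FEV1 fall and recover together, DCR is tracking lung function, and nothing limits Part C to stable-state change. This also stands. A reader might infer that the correlation is simply spurious; the documents do not support that. It misleads only when read as long-term lung health or prediction, which the protocol's rationale gives as the purpose.
- **The inputs are assumed.** The 20% is a recruitment estimate. If annual reviews were already deferred during exacerbation, p is lower, and clustering of exacerbations within people would lower the correlation between earlier films. At d of 0.5 or less the effect on the correlation is small. All true; the size is open.
- **The only named analysis uses baseline DCR.** The figures above model change against change and do not size the baseline analysis. The stated aim, however, is about changes.
- **The study is exploratory.** That lowers the stakes, but a 0.05 threshold is still applied, and hypotheses drawn from mixed states are hard to interpret.

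Annual-review spirometry and DCR were also not simultaneous, which is a separate comparability problem for the Part B film and does not remove this one.

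**Conclusion.** The concern holds as a risk of unknown size. As written, Part C can combine films taken in exacerbation with stable ones, and nothing in the plan would let the analyst tell them apart. On the assumed 20%, the induced correlation is negligible to small at d = 0.5 and material from about d = 1; at 5% it is at most about 0.10 into the Part B film over the range shown. All these figures require that exacerbation lowers FEV1 as well as the DCR measures, and the documents report only the DCR response to treatment.

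Two stronger readings should be resisted. One is that the mismatch between the Part B film and the earlier films causes both effects. It causes only the mean shift: the induced correlation at d = 1 is 0.24 between two unrestricted films and 0.14 into the restricted one. The other is that films from the centre's earlier exacerbation study enter the series. The protocol points to annual-review films and does not say that those others will be used. The wording on current imaging is itself ambiguous, but the Part C heading, a retrospective review of longitudinal data, supports reading it as films already held.

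**What to change.** For every Part C film, including the Part B film, take from the clinical record the exacerbation status on the day and any exacerbation treatment in a fixed preceding window. Use one written definition for all films; the protocol does not currently define exacerbation.

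Then report the longitudinal and the baseline DCR–marker relationships in two ways: for films that are exacerbation-free and outside the treatment window, and for all films (or with status as a film-level covariate). State in advance which of these the conclusion on long-term lung health rests on. Aligning the rule only for changes into the Part B film would not be enough, because the correlation also arises between earlier films.

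The cost is record review for films already held, a short addition to the protocol, and fewer films in the restricted analysis. No new imaging or visits are needed.
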